## 9.4.2 BICR Confirmation of Progression (Part 2)

Following the final analysis, images will no longer be submitted to BICR for evaluation. Imaging should be performed per institutional standard of care.

Until final analysis, sites should submit all scans to the central imaging vendor on a rolling basis, throughout the duration of the study. BICR of scans will occur on a rolling basis, blinded to treatment arm, clinical data, and investigator assessment of submitted scans. For Part 2, when progression per RECIST 1.1 criteria is assessed by the investigator, the site will inform the central imaging vendor, in order for BICR assessment of progression to be performed. The BICR will be completed and the results provided to the site as specified in the imaging vendor documents, provided there are no pending imaging queries to the site. All details on the timelines and associated process requirements will be outlined in the Imaging Manual.

Participants whose progression is not confirmed by the BICR will be required to continue tumor assessments (if clinically feasible) according to the protocol-specified schedule, or sooner if clinically indicated. Also, if participants discontinue treatment without radiographic progression, tumor assessments will continue according to the protocol-specified schedule, as noted in Section 2 (Schedule of Activities) until progression has been confirmed by BICR.

All study treatment decisions will be based on the investigator's assessment of tumor images and not on the BICR assessment.

## 9.5 Pharmacokinetics and Immunogenicity Assessments

Following the final analysis, PK and IMG samples will no longer be collected.

Pharmacokinetic (PK) and immunogenicity (IMG) assessment data for BMS-986253, nivolumab, and ipilimumab will be collected from study participants assigned to the study at the time points indicated

All time points are relative to the start of the first drug administration on that day. All on-treatment time points are intended to align with days on which study drug is administered; if dosing occurs on a different day, the PK and IMG sampling should be adjusted accordingly. If it is known that a dose is going to be delayed, then the predose sample should be collected just prior to the delayed dose. However, if a predose sample is collected but the dose is subsequently delayed, an additional predose sample should not be collected. All predose samples should be taken within 30 minutes before the start of any dose infusion. End of infusion (EOI) samples should be taken immediately prior to completion of the infusion, preferably within 2 minutes. Blood samples should be drawn from a site other than the infusion site (ie, contralateral arm) on days of infusion.

Pharmacokinetics of BMS-986253 will be derived, if feasible, from serum concentration versus time data following administration of BMS-986253. PK parameters that will be assessed are shown below:

Table 9.5-1: Pharmacokinetic Parameters

Cmax	Maximum observed serum concentration
Tmax	Time of maximum observed serum concentration
AUC(0-T)	Area under the serum concentration-time curve from time zero to time of last quantifiable concentration; may be calculated if concentrations are not quantifiable up to TAU across a treatment group
AUC(TAU)	Area under the serum concentration-time curve in 1 dosing interval
Ctau	Observed serum concentration at the end of a dosing interval
Ctrough	Trough observed serum concentrations (this includes pre-dose concentrations [C0] and Ctau)

[figure not shown]
Table 9.5-2: Pharmacokinetic Parameters that May be Assessed Following the Administration of BMS-986253

CLT	Total body clearance
Css-avg	Average serum concentration over a dosing interval (AUC[TAU]/tau) at steady state
AI	Ratio of an exposure measure at steady state to that after the first dose (exposure measure includes AUC[TAU] and Cmax)

Abbreviations: AUC(TAU), area under the serum concentration-time curve in 1 dosing interval; Cmax, maximum observed plasma concentration; tau, dosing interval.

Individual participant PK parameter values will be derived by non-compartmental methods using a validated PK analysis program (Part 1 only). Actual times will be used for all formal analyses.

Sparse nivolumab and ipilimumab concentration-time data will be collected and may be used in an integrated population pharmacokinetics (PPK) or exposure response analysis along with data from other studies, which will be the subject of a separate report. Separate samples will be collected for PK and IMG assessments.

Protocol Amendment No.: 07

Date: 17-May-2024

Approved v 8.0 930120018 9.0

Protocol Amendment No.: 07 Date: 17-May-2024

Approved v8.0 930120018 9.0

CA027002

Anti-IL-8

[figure not shown]

Protocol Amendment No.: 07 Date: 17-May-2024

Approved v8.0 930120018 9.0

Protocol Amendment No.: 07

Immunogenicity samples will be analyzed for anti-nivolumab/anti-ipilimumab/anti-BMS-986253 antibodies by validated bioanalytical method(s). Immunogenicity samples positive for any anti-nivolumab, anti-ipilimumab, or anti-BMS-986253 antibodies may be analyzed for neutralizing antibodies by validated bioanalytical method(s). Exploratory results will not be reported. Bioanalytical samples designated for assessments (eg, immunogenicity, PK, or biomarker) from the same collection time point may be used interchangeably for analyses, if required (including but not limited to insufficient volume for complement assessment, to follow-up on suspected immunogenicity related AE, etc). For all PK and immunogenicity plasma/serum samples, the date and actual time collected must be recorded. For participants whose only peripheral access is via a venous access device or peripherally inserted central catheter, refer to the Laboratory Manual for the proper technique to ensure undiluted whole blood for PK assessments.

Further details of sample collection, processing, and shipment will be provided in the laboratory procedures manual.

## 9.6 Pharmacodynamics

Details on pharmacodynamic biomarker assessments are in Section 9.8.2.1.

## 9.7 Pharmacogenomics

Not applicable.

# 9.7.1 Absorption, Distribution, Metabolism, and Excretion Sampling

Not applicable.

#### 9.8 Biomarkers

Following the final analysis, biomarker samples will no longer be collected.

[figure not shown]

If biomarker samples are drawn but study treatment(s) is not administered, samples will be retained. A detailed description of each biomarker sample analysis and assessment is described below, and a schedule of biomarker sample collections is provided

Further details of blood, serum, and tumor tissue collection and processing will be provided to the site in the procedure manual.

## 9.8.1 Serum IL-8 Levels for Participant Selection

Previous studies have demonstrated that changes in serum IL-8 levels are associated with response to nivolumab or pembrolizumab in patients with metastatic melanoma and NSCLC. In addition, it has been shown that early changes in serum IL-8 levels post-treatment can predict response and OS. It has also been demonstrated that expression of CXCR2, one of two IL-8 receptors, is upregulated in metastatic melanoma lesions that progressed following treatment with nivolumab compared to lesions from the same patient that regressed during nivolumab treatment. Finally, a relatively high median level of serum IL-8 at baseline has been shown to correlate with OS in melanoma, NSCLC, and RCC patients in response to ipilimumab. In light of these findings and of the concept that BMS-986253 can compromise IL-8-mediated immunosuppression, serum IL-8 levels at baseline could conceivably be used as a biomarker to select participants more likely to benefit from nivolumab when combined with BMS-986253.

IL-8 is provided in Section 5.4.3. Any further segregation will be based upon post-hoc allocation of participants into intermediate or low- versus high-expression categories based upon IL-8 level cut-offs determined from the aforementioned analyses but inclusion will be based solely upon the Clinical Laboratory Improvement Amendments-certified analytical cut-off.

Protocol Amendment No.: 07

Approved v 8.0

930120018 9.0

161

Protocol Amendment No.: 07

Approved v8.0

[figure not shown]
930120018 9.0

Protocol Amendment No.: 07

Protocol Amendment No.: 07 Date: 17-May-2024

Approved v8.0 930120018 9.0

Date: 17-May-2024

Approved v 8.0 930120018 9.0

[figure not shown]
Protocol Amendment No.: 07

Protocol Amendment No.: 07 Date: 17-May-2024

[figure not shown]
Approved v8.0 930120018 9.0

Clinical Protocol CA027002 BMS-986253 Anti-IL-8

Protocol Amendment No.: 07

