## 5.1.2 Screening Period

The screening period will be up to 28 days and begins by establishing the participant's initial eligibility and signing of the informed consent form (ICF). In order to establish eligibility for this study, participants will undergo baseline physical examinations, vital signs and oxygen saturation measurements, 12-lead electrocardiogram (ECG), and clinical laboratory evaluations.

If a participant exceeds the 28-day screening period (eg, waiting for a laboratory value), the participant must be reconsented, but does not require a new participant identification number. The fewest number of procedures from the initial screening should be repeated to qualify the participant, while maintaining participant safety and eligibility. Repeat serum IL-8 testing will not be required if the previous sample was obtained within 42 days of study treatment initiation.

Assignment to a Study Part 1 (1A, 1B, or 1C) must be designated in the IRT system prior to the participant's assignment to a dosing regimen. In Part 2, all participants will be randomly assigned to Arm 2A (BMS-986253 + nivolumab + ipilimumab) or 2B (placebo + nivolumab + ipilimumab). Prior to randomization in Part 2, screening laboratory test results for serum IL-8 and LDH must be received, and must be entered in the electronic case report form (eCRF). Part 2 of the study is double-blind; the participant, Sponsor, and site staff (except as indicated in Section 7.5) will not be aware of treatment/cohort assignment, as described in Section 7.4.

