# 3) Physical and Laboratory Test Findings

Participants must have:

- a) Baseline (only required for Part 1A and Part 1B)
- b) Adequate hematologic function as defined by the following:
  - i) Neutrophils  $\geq 1,500 \mu L$
  - ii) Platelets  $\geq 80 \times 10^3/\mu L$  (transfusion to achieve this level is not permitted within 2 weeks of first study treatment administration)
  - iii) Hemoglobin  $\geq 8$  g/dL (transfusion to achieve this level is not permitted within 2 weeks of first study treatment administration)
- c) Adequate hepatic function
  - i) Alanine aminotransferase (ALT) and aspartate aminotransferase (AST)  $\leq$  3× upper limit of normal (ULN)
  - ii) Total bilirubin  $\leq 1.5 \times$  ULN (except participants with Gilbert's Syndrome who must have normal direct bilirubin)

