If PK, pharmacodynamic, and/or safety analyses indicate further assessment of a dosing regimen is not warranted and/or assessment of additional dosing regimens is indicated, then randomization will be stopped, and subsequent participants will be assigned sequentially to dosing regimens available at that time. If any dosing regimen evaluates a higher dose of BMS-986253 than previously explored, an initial 4-participant safety lead-in with a 28-day DLT period will be required. Approximately participants will be dosed in the dosing regimen(s) of interest. Additional exploration of a specific dosing regimen may be warranted, in which case a maximum of approximately additional participants will be assigned to a dosing regimen of interest in Part 1B. A maximum of approximately participants will be dosed in Part 1B.

Part 1C is a safety evaluation of BMS-986253 in combination with nivolumab and ipilimumab. Part 1C will begin once the DLT period is completed for Cohort 1B6 (BMS-986253 3600 mg Q2W + nivolumab 480 mg Q4W), and will enroll simultaneously with Part 1B. In Part 1C, participants

Protocol Amendment No.: 07 Date: 17-May-2024

Protocol Amendment No.: 07

#### Part 2

Part 2 will begin after determination of the RP2D from Part 1 and generating safety data on the triplet combination of BMS-986253 plus nivolumab plus ipilimumab in Part 1C. Part 2 is a double-blind randomized evaluation of BMS-986253 plus nivolumab plus ipilimumab versus placebo plus nivolumab plus ipilimumab and will be conducted to evaluate the efficacy of BMS-986253 in participants who are refractory to anti-PD-(L)1 therapy.

IRT will be used to track the enrollment number.

Once assigned a subject ID in IRT, participants that have met all eligibility criteria will be randomized through IRT (up to 3 days prior to C1D1). The following information is required prior to participant randomization:

- Participant subject ID
- Date of birth
- Gender
- Screening serum IL-8 level

• Screening LDH

Participants will be randomized in a 1:1 ratio to treatment and control arms. Three stratification factors will be used during randomization: screening

and screening LDH (≤ ULN or > ULN). Screening serum IL-8 data will be transferred directly from the analyzing laboratory to IRT. BRAF status and screening LDH must be entered in eCRF by the site.

Approximately participants will be randomized in Part 2.

The exact procedures for using the IRT will be detailed in the IRT manual.

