## 10.3.1 Efficacy Analyses

The main efficacy analyses will be performed on the efficacy population for the final analysis. Efficacy analyses based on the response-evaluable population may be performed for interim analyses (as per Section 10.3.8). Efficacy analyses may be performed on selected subgroups, including biomarker-selected subgroups. Efficacy analyses will be performed using the RECIST v1.1 criteria. Additional details on efficacy analyses are provided in Table 10.3.1-1.

Table 10.3.1-1: Part 1 Efficacy Analysis

Endpoint	Statistical Analysis Methods
ORR is defined as the proportion of participants whose BOR is either CR or PR in the population of interest.	Estimate of ORR and corresponding two-sided exact 95% CI using the
BOR for a participant will be assessed per RECIST v1.1 by investigator, otherwise specified	treatment for each tumor type
DOR  DOR for a participant with a BOR of CR or PR, is defined as the time between the date of first response and the date of the first objectively documented tumor progression per RECIST v1.1 or death, whichever occurs first.	Median duration of response using and corresponding two-sided 95% CI using Brookmeyer and Crowley methodology (using log-log transformation) by treatment for each tumor type

Abbreviations: BOR, best overall response; CI, confidence interval; CR, complete response; DOR, duration of response; ORR, objective response rate; PR, partial response; RECIST, Response Evaluation Criteria in Solid Tumors.

Table 10.3.1-2: Part 2 Efficacy Analysis

The approach to handling events such as subsequent cancer

therapy will be consistent between ORR and DOR.

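### If Part 2 efficacy is examined by baseline serum IL-8, the only visible method is a low/intermediate versus high split; a treatment-by-log(IL-8) interaction would keep more information

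*Combined protocol and SAP*

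**What the plan says.** Section 9.8.1 raises the idea that "serum IL-8 levels at baseline could conceivably be used as a biomarker to select participants more likely to benefit from nivolumab" given together with BMS-986253. It then states: "Any further segregation will be based upon post-hoc allocation of participants into intermediate or low- versus high-expression categories". The cut-offs are to come from analyses mentioned earlier in the text, and the sentence ends by setting this apart from eligibility: "but inclusion will be based solely upon the Clinical Laboratory Improvement Amendments-certified analytical cut-off".

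The eligibility cut-off belongs to Part 1. In Section 6.1, criterion 3a reads "Baseline (only required for Part 1A and Part 1B" (the analyte is blacked out there, but the Protocol Summary and Section 5.1.1 show that it is serum IL-8). Sections 1 and 5.4.3 say that Part 2 takes participants at any IL-8 level.

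The value is nevertheless held for every randomized Part 2 participant. Section 5.1.2 states "Prior to randomization in Part 2, screening laboratory test results for serum IL-8 and LDH must be received", and Section 7.4 states "Screening serum IL-8 data will be transferred directly from the analyzing laboratory to IRT". IL-8 is also a stratification factor, with its levels not visible.

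On analysis, Section 10.3.1 says "Efficacy analyses may be performed on selected subgroups, including biomarker-selected subgroups". Section 10.3.5 summarises IL-8 numerically (absolute values, changes and geometric mean ratios over time) and does not relate it to efficacy. Section 10.3 leaves detail to an SAP that is to be finalised before database lock.

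**The concern.** Baseline IL-8 is known to be prognostic: Sections 3.1, 5.4.1 and 5.4.9 say so, and the rationale for Amendment 07 links it to tumor burden. Whether it also predicts benefit from BMS-986253 is a separate question. Part 2 is the only comparison in the study against a control without that drug, so it is the only place where the two roles can be told apart.

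The direct way to ask is to test whether the treatment effect changes with IL-8. Results shown category by category do not test that. They also treat unlike values within a category as equal, and close values on either side of the cut as different. When the underlying relation is smooth, this costs power, and the answer can shift with the position of the cut. No cut-off is visible.

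**Working it through.** The plan states no power, cut-off or expected precision for an IL-8 analysis, and the Part 2 sample size is blacked out, so there is no figure to reproduce. The size below is conditional on assumptions.

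**Information kept by one cut.** Assume log IL-8 is standard normal, X, and that the interaction is linear in X. With a share p called high and cut c = z(1−p), the information kept relative to the continuous value is the squared correlation between X and the indicator X > c:

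E = φ(c)² / [p(1−p)]

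The power that remains, for a test with 80% power on the continuous value at two-sided 5%, is Φ[(1.960 + 0.842)·√E − 1.960].

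| Split | φ(c) | E | Information lost | 80% power becomes |
|---|---|---|---|---|
| 50/50 | 0.3989 | 0.1592/0.25 = 0.637 (= 2/π) | 36.3% | 61% |
| 33/67 | 0.3636 | 0.1322/0.2222 = 0.595 | 40.5% | 58% |
| 25/75 | 0.3178 | 0.1010/0.1875 = 0.539 | 46.1% | 54% |
| 20/80 | 0.2800 | 0.0784/0.16 = 0.490 | 51.0% | 50% |

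**Three equal groups.** The outer groups have means ±0.3636/(1/3) = ±1.091 and the middle group has mean 0. Between-group variance is (2/3)(1.091²) = 0.793, so 20.7% is lost and 80% power becomes 70%.

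**Other shapes.** A uniform variable cut at its median loses 25%. If the effect is linear on a skewed raw scale (log-normal, log SD 0.5 to 1.0, high share 25% to 50%), the loss is 39% to 73%. If benefit truly steps at the cut, the categories lose nothing.

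**Simulated power for the interaction on ORR.** Control ORR was set at 30%, following the 29% and 31% cited in Section 5.4.8. The model was logit(response) = log(0.3/0.7) + 0.3t − 0.3x + 0.9tx, with 1:1 allocation, a two-sided 5% test and 1,500 trials per cell (simulation error at most √(0.25/1500) ≈ 1.3 points). Total N and the interaction of 0.9 log-odds per SD are assumptions.

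| Total N | Truth | Continuous | Median split |
|---|---|---|---|
| 100 | linear | 53% | 35% |
| 150 | linear | 71% | 51% |
| 200 | linear | 81% | 64% |
| 150 | step at the cut | 51% | 72% |

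**Dependence on the interaction size.** A second simulation used logit(response) = −0.85 − 0.4x + 0.5t + g·tx, a likelihood-ratio test, and 40, 60 or 80 per arm. At 60 per arm, continuous versus median split gave 43% versus 29% for g = 0.7, and 70% versus 53% for g = 1.0. For g = 0.5 the gain from the continuous value was only about 6 to 9 points across the three arm sizes. With no interaction, both methods rejected in about 5% to 7% of trials, so the gain does not come from an inflated error rate.

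**The case against.** The strongest reply is that the documents do not commit to the analysis criticised here. Section 9.8.1 is about participant selection; the sentence names neither Part 2 nor efficacy nor any test, and it sits beside an inclusion cut-off that applies only to Parts 1A and 1B. Section 10.3.1 is optional and names no biomarker, cut or model. This stands. A reader might infer that Part 2 efficacy is definitely to be analysed by IL-8 category, but that link is an inference. The partial answer is that the sentence contrasts further segregation with inclusion, so it covers participants already enrolled, and it follows directly on the idea of IL-8 as a marker of benefit.

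A reader might also infer that the cut will be tuned to Part 2 outcomes. The text does not support this. The after-the-fact element describes the allocation of participants, while the cut-offs come from analyses mentioned earlier, which are partly blacked out. Because IL-8 is a stratification factor, some category may have been fixed before randomization.

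Nor can it be said that the plan lacks a continuous model. Text around Sections 9.8.1 and 10.3.5 is missing, as are the exploratory objectives for Part 2, and Section 10.3 describes an SAP still to be developed.

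Finally, a step truth reverses the power ranking (51% continuous versus 72% categorised at N = 150). That also stands, and is the reason for the spline check and for keeping the categories on display.

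**Conclusion.** The point holds in conditional form and is minor. Categories are the only visible method for separating participants by baseline IL-8, and a better one is available on data already held. If Part 2 efficacy is examined through a single cut, the loss of interaction information is about 36% at the median and up to about 51% at a 20/80 split, given a normal log scale and a linear effect. A flat statement that a third of the information is thrown away would go too far: the cut-off is not visible, three equal groups lose about 21%, and a true step at the cut loses none. The power figures rest further on assumed arm and interaction sizes.

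The primary analysis, BICR-assessed ORR in all randomized participants, is unaffected. Amendment 07 itself lowers the relevance of IL-8 for selection, so this concerns exploratory work only.

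**What to change.** In the SAP, with Section 9.8.1 aligned, state that if Part 2 efficacy is examined by baseline IL-8:

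- the lead exploratory analysis is a treatment-by-log(screening IL-8) interaction, by logistic regression for BICR-assessed ORR and by a Cox model for PFS;
- a restricted cubic spline checks the linear form, and the estimated treatment effect is shown across the IL-8 range;
- one stated rule handles values below the assay limit;
- any cut-off is fixed before unblinding, and the low/intermediate and high categories serve as a descriptive display.

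The cost is a few lines of SAP text and two extra models on values already collected, with no new visits, samples or participants. The downside is some loss of power if the true effect is a sharp step at the cut. If the SAP or the blacked-out text already contains such a model, only the wording of Section 9.8.1 needs aligning.

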# 9.8.4 Additional Research Collection

This protocol will include residual sample storage for additional research.

Protocol Amendment No.: 07

#### For All US sites:

Additional research participation is required for all investigational sites in the US.

